Interventional Template Version: 12 February 2020

US	United States
UP	Unanticipated problem
VAS	Visual analog scale
WOMAC	Western Ontario and McMaster Universities Osteoarthritis index
WOMRS	Whole-Organ Magnetic Resonance Imaging Score

CONFIDENTIAL

Protocol Summary

[figure not shown]
Title	Genicular Artery Embolization for Treatment of Knee Osteoarthritis (OA)
Short Title	Geniculate Artery Embolization for Treatment of Knee Osteoarthritis
Brief Summary	Single-arm, single-center, no sham or placebo, prospective pilot trial designed to evaluate the feasibility and safety of transcatheter arterial embolization in patients with knee OA. Eligible participants will receive geniculate artery embolization using Embosphere™ Color-Advanced Microspheres. Patients will be followed up for a total of 12 months.
Objectives	Primary objective: to determine the effectiveness of genicular artery embolization in reducing knee pain at 3-months post intervention in patients with knee OA. This will be assessed by evaluating the clinical success rate defined as at least 50% reduction in Western Ontario and McMaster Universities Osteoarthritis index (WOMAC) pain score from pre-intervention baseline to follow-up visit at 3 months post-intervention without an increase in baseline incidence of pain medication use or intra-articular injection. The WOMAC Score will be calculated from the Knee injury and Osteoarthritis Outcome Score (KOOS) score. Secondary objectives: 
 - To evaluate the safety of genicular artery embolization - To determine whether transcatheter arterial embolization improves OA-related knee symptoms and quality of life.
Methodology	Prospective, single-arm, single-center, no sham or placebo, pilot study
Endpoint	Primary endpoint: WOMAC pain score at 3-months post intervention. Secondary endpoints: 
 - Rate, type, causality, and severity of adverse events - WOMAC pain score at 1-, 12-, and > 12-months post intervention - Pain visual analog scale (VAS) - WOMAC knee stiffness and physical function scores at 1, 3, 12 months
Study Duration	3 years
Participant Duration	Each individual subject will be enrolled for approximately 13 months to complete all study visits from the initial screening visit to last follow up at 12-months post intervention. Participants that completed the 12 months visit by August 31, 2024 will be invited to participate in longer follow up (18 months – 48 months follow-up).

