4.1 Description of Study Design

This study is a single-center, single arm, no sham or placebo, open label, prospective pilot study designed to evaluate the safety and feasibility of geniculate artery embolization for the treatment of knee OA. Enrolled patients will receive angiography and embolization of the one or more geniculate arteries in the affected knee using 250 µm Embosphere microspheres. If both knees are affected, the knee with the higher pain score on electronic VAS will be targeted.

The primary objective is to evaluate the effectiveness of geniculate artery embolization in reducing knee pain at 3 months. The primary objective will be evaluated by the clinical success rate. Clinical success is defined as at least 50% reduction in WOMAC pain score at 3-month follow up visit. 40 patients will be required for this study. The study would accrue 50 patients to account for an attrition rate of 20%.

Change in WOMAC pain score and pain VAS will be used as a measure of efficacy (i.e., pain reduction).

WOMAC questionnaire is a widely used, disease-specific measure for knee OA. It includes 24 questions on daily activities. WOMAC pain score includes five questions regarding pain (pain during walking, stair climbing, nocturnal, rest, weight bearing); each question will be scored using the

CONFIDENTIAL

following points: 0 for no pain, 1 for mild, 2 for moderate, 3 for severe, and 4 for extreme pain. possible score ranges for pain are 0–20. For this purpose, WOMAC Score will be calculated from the Knee injury and Osteoarthritis Outcome Score (KOOS) score which was developed as an extension of the WOMAC score with the purpose of evaluating short-term and long-term symptoms and function in subjects with knee injury and osteoarthritis. This means that the KOOS questionnaires will be administered to patients during visits and the WOMAC score will be calculated from the KOOS scores later at the time of data analysis.

The electronic VAS is a horizontal line with no markings on the scale except “No pain” on the left (score: 0 mm) and “worst possible pain” on the right end of the scale (score: 100 mm). Subjects mark the VAS to indicate their current pain level, with 0 mm representing “No pain” and 100 mm representing “worst possible pain”. In our study, subjects will be asked to mark their pain level on a paper VAS on study questionnaire form and will give a score between 0 to 100, which will be documented on the appropriate eCRF.

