4.2 Study Endpoints

4.2.1 Primary Study Endpoints

The primary endpoint is WOMAC pain score at 3 months post intervention.

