5.2 Exclusion Criteria

An individual who meets any of the following criteria will be excluded from participation in this study:

1. Active systemic or local knee infection or;
2. Active malignancy or;
3. Life expectancy less than 12 months or;
4. Prior ipsilateral knee surgery (within 3 years of baseline visit), arthroscopic surgery (within 6 months of baseline), total or partial knee replacement regardless of timing or;
5. Ipsilateral knee intra-articular injection in the last 3 months or;
6. Rheumatoid arthritis, spondyloarthropathies, crystal disease, gout, pseudogout, or lupus;
7. Pregnant during the study period or;
8. Renal dysfunction as defined by serum creatinine > 1.6 dl/mg or eGFR < 60 on blood tests obtained within 30 days of procedure or;
9. Body weight greater than 200 Kg or;
10. Uncorrectable coagulopathy (platelet count $< 50,000$, international normalized ratio > 1.5 within 30 days of procedure; or
11. Known history of contrast allergy resulting in anaphylaxis or;
12. Known significant arterial atherosclerosis that would limit selective angiography and/or lower extremity symptoms thought to be secondary to arterial vascular disease (eg claudication, ischemic rest pain)
13. Post-traumatic knee (if trauma occurred within 12 months of baseline or was associated with fractures)
14. known avascular necrosis in the target knee
15. Contraindications to MRI such as such as claustrophobia, metallic fragment/implants, pacemaker.

CONFIDENTIAL

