7.1 Study Procedures/Evaluations

7.1.1 Study Specific Procedures

- Medical history
 - Complete medical history will be obtained from medical records if available and/or by interview during clinic visits.
- History of previous and concomitant treatment
 - Knee injections and frequency over the 12 months
 - Medication history over the last month will be obtained during pre and post intervention study visits. Medication history will focus on medications currently taken for the treatment of knee OA; including prescription and over-the-counter medications for pain.
 - Physical therapy and frequency over the 12 months
 - Weight loss / gain
- Focused physical examination:
 - Vital signs (temperature, blood pressure, heart rate, oxygen saturation, height, weight, BMI)
 - Focused knee examination.
 - Lower extremity pulses
- Imaging assessment with knee MRI
 - Baseline and follow-up (at 3 months) knee MRI will be performed.
 - Knee MRI protocol will include: Axial t2 FS, Sagittal PD, Sagittal T2 FS, Coronal PD FS, Coronal PD FS, non-contrast axial and sagittal T1 FS.
 - Imaging variables collected for this study is found in the attached eCRFs
- A discussion of the results of any study specific procedures (e.g., radiographic or other imaging or laboratory evaluations) will be provided to participant after the completion of the study unless these information represent a significant health-related issue.
- Laboratory tests:
 - Baseline and follow-up (at 1-, 3-, and 12-, 18-48 months) laboratory tests will be obtained
- Administration of questionnaires or other instruments for patient-reported outcomes:
 - Electronic VAS
 - KOOS questionnaire
 - Self-reported quality of life EQ-5D-5L questionnaire

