10.4.1 General Approach

This is a single arm study (i.e., no sham, placebo or alternative treatment included). The primary objective (clinical success rate) will be assessed as a binary outcome of whether or not each patient shows at least a 50% reduction in WOMAC pain scores from baseline (pre-treatment) to post-treatment follow-up at 3 months without an increase in baseline incidence of pain medication use or intra-articular injection. The response rate will be summarized in terms of the observed proportion of patients manifesting a positive response and a two-sided exact 95% confidence interval (CI) per the Blyth-Still-Casella method. WOMAC pain score, pain VAS, WOMAC stiffness and physical activity scores will be assessed as mean and standard deviation.

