10.4.2 Analysis of the Primary Endpoint(s)

The primary endpoint is the clinical success rate defined as at least 50% reduction in WOMAC pain score at 3-month follow-up compared to baseline as a binary assessment.

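### The primary endpoint is defined three ways in the current text and none is said to govern, so a patient with added medication or an injection can be a success or a failure

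*Combined protocol and SAP*

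**What the plan says.** The current text holds three versions of the primary endpoint.

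- **Composite.** At least a 50% fall in WOMAC pain from baseline to 3 months, "without an increase in baseline incidence of pain medication use or intra-articular injection". This is in the Protocol Summary objective, section 3.1 and section 10.4.1.
- **Pain only.** Section 4.1: "Clinical success is defined as at least 50% reduction in WOMAC pain score at 3-month follow up visit". Section 10.4.2, which is headed as the analysis of the primary endpoint, says clinical success is "defined as at least 50% reduction in WOMAC pain score at 3-month follow-up compared to baseline as a binary assessment". Section 10.2, which sets the hypotheses and the count needed to reject, uses the same pain-only criterion.
- **Score with no threshold.** Section 4.2.1: "The primary endpoint is WOMAC pain score at 3 months post intervention". The Summary endpoint row says the same: "Primary endpoint: WOMAC pain score at 3-months post intervention".

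Section 10.1 states that no formal SAP will be prepared before database lock.

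On the data behind the condition, section 7.1.1 records "Knee injections and frequency over the 12 months" and medication history over the last month. Section 5.2 excludes patients with "Ipsilateral knee intra-articular injection in the last 3 months or". Sections 7.3.2, 7.3.4 and 7.4 require pain medication to be withheld for 24 hours before each pain evaluation.

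**The concern.** Composite responders are a subset of pain-only responders. The pain-only rate can therefore never be the lower of the two, and it exceeds the composite rate by exactly the share of patients who reach the 50% fall but add medication or have an injection. Such a patient is a success under 10.2 and 10.4.2 and a failure under 3.1 and 10.4.1. With no control arm, relief that came from added treatment would be counted in favour of embolization.

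The trial is open label, and section 1 gives the principal investigator responsibility for both data collection and statistical analysis. If the definition stays open, it can be settled when the outcomes are already known.

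The composite also cannot be applied as it stands. It has no patient-level rule for what counts as an increase and no comparison window.

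**Working it through.** **1. Where each version appears**

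| Place | At least 50% fall | No increase in medication or injection |
|---|---|---|
| Summary objective, 3.1, 10.4.1 | yes | yes |
| 4.1, 10.2, 10.4.2 | yes | not mentioned |
| Summary endpoint row, 4.2.1 | not mentioned | not mentioned |

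The Summary contradicts itself, and so does section 10.

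**2. The plan's own figures**

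Inputs from 10.2 and 10.5: null rate 0.50, alternative 0.75, n = 23, reject at 16 or more responders.

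Formula: P(X ≥ r | n, p) = Σ from k = r to n of C(n,k) p^k (1 − p)^(n − k).

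- P(X ≥ 16 | 23, 0.50) = 0.0466; the plan states 0.047.
- P(X ≥ 16 | 23, 0.75) = 0.8037; the plan states 80.4%.
- 23/0.8 = 28.75, rounded up to 29; 40/0.8 = 50. Both match.

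The design arithmetic is right. It does not say which responder is being counted.

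**3. Effect of the definition**

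The documents give no rate of added medication or injection, so the rates below are assumptions. The plan states no rejection count for 40 patients. I use 26 of 40, the smallest count with one-sided alpha at or below 0.05 (26 gives 0.040, 25 gives 0.077).

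*(a) True composite rate at the null of 0.50, scored by the pain-only definition*

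| Pain-only rate | P(reject), 16/23 | P(reject), 26/40 (assumed rule) |
|---|---|---|
| 0.50 | 0.047 | 0.040 |
| 0.55 | 0.115 | 0.133 |
| 0.60 | 0.237 | 0.317 |

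*(b) Pain-only rate 0.75 (assumed), scored by the composite.* A share q of pain responders fails the added condition, so the composite rate is 0.75 × (1 − q).

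| q | Composite rate | Power, 16/23 | Power, 26/40 (assumed rule) |
|---|---|---|---|
| 0 | 0.75 | 0.804 | 0.946 |
| 0.05 | 0.7125 | 0.668 | 0.852 |
| 0.10 | 0.675 | 0.515 | 0.699 |

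**4. The undefined window**

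Take a patient with one target-knee injection 6 months before entry and one between embolization and month 3.

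- Raw counts, 12 months before against 3 months after: 1 against 1, no increase, condition met.
- Monthly rates: 1/12 = 0.083 against 1/3 = 0.333, an increase, condition failed.
- Matched 3-month windows: 0 (by the section 5.2 exclusion) against 1, an increase, condition failed.

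The text does not choose among these.

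**The case against.** The best defence is that 10.4.2 is shorthand for 10.4.1, which sits just above it and keeps the condition. This has some force: section 10 contradicts itself but does not drop the condition throughout. It does not settle the matter, because 10.4.2 states a definition and 10.2, which fixes the rejection count, uses the same shorter criterion.

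A reader might infer more than the documents support on four points.

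- *Pain-only scoring simply credits embolization with analgesic relief.* The 24-hour withholding limits acute masking at the visit. It does not cover injections or heavier use over the preceding month, so only part of this inference stands.
- *The composite misfires for injections.* That follows only from comparing raw counts over unequal windows. Section 7.1.1 does not make 12 months the comparator for the primary endpoint; the 12-month comparison in 3.2 belongs to a secondary objective. The supportable statement is that the window is undefined.
- *The composite necessarily costs power.* It does so only if 0.75 was meant as the pain-only rate. Section 10.5 ties 0.75 to an unspecified positive response; if the composite was meant, nothing is lost.
- *The 26/40 figures are the plan's operating characteristics.* They are not; 16 of 23 is the only stated rule. That it was not updated for 40 patients is a separate matter.

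**Conclusion.** The concern holds as a conflict of definitions together with an undefined comparison. The quantity that decides success has three versions, none is named as governing, and no later SAP is planned to resolve it.

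The direction is certain: pain-only scoring can only raise the success rate. The size is not known. Under the stated 16/23 rule it is a rejection probability of 0.115 to 0.237 instead of 0.047 when the composite rate is 0.50 and the pain-only rate is 0.55 to 0.60. In the other direction, power is 0.668 to 0.515 instead of 0.804 when 0.75 is the pain-only rate and 5% to 10% of pain responders fail the composite. The conclusion is the same under an assumed 26/40 rule. The documents do not show that any version has been chosen after seeing data, only that the text leaves that possible. This should be corrected before analysis.

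**What to change.** 1. Carry the composite of 3.1 and 10.4.1 into the Summary endpoint row and sections 4.1, 4.2.1, 10.2 and 10.4.2. The Summary objective already has it.
2. Define an increase per patient with matched windows. For medication, compare 30-day pain medication use at the 3-month visit with 30-day use at baseline, the period already named in 3.2. For injections, count any target-knee injection between day 0 and the 3-month visit as an increase, since the section 5.2 exclusion makes the matched 3-month baseline zero for that knee.
3. Report the pain-only responder rate as a sensitivity analysis.

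The cost is mainly wording. Medication history and previous or concomitant treatments are scheduled at baseline and at 3 months. The case report forms are not in the documents, so confirm that they capture 30-day use and injection dates. Finer rules, such as counting analgesic days or a move to a stronger class, are optional and depend on what those forms hold. The downside is a possibly lower success rate, and lower power if 0.75 was meant for pain-only response.

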10.4.3 Analysis of the Secondary Endpoint(s)

Analysis of secondary endpoints include: (1) changes in the mean WOMAC and VAS pain scores, the mean WOMAC knee stiffness and physical function scores and the total WOMAC knee physical function score; (2) the technical success rate (defined as the proportion of patients for whom the procedure was successfully completed); (3) the adverse event rate (defined as the proportion of patients showing each type of adverse event or any adverse event); (4) reduction in the usage of pain medication, the frequency of infection therapy, the need for physical therapy; and (5) the proportion of patients showing synovial thickening, joint effusion, meniscus tear, synovial enhancement, osteophytes. A point estimate and 95% confidence interval will be provided for each secondary outcome at each time and for the change in each outcome from baseline to each post-treatment follow-up visit. Changes in the outcomes from baseline to follow-up will be tested using the paired-sample Wilcoxon signed rank test for the WOMAC and VAS scores and the McNemar test for the other measures which will be assessed as binary outcomes (e.g., whether or not the patient reported usage of pain medication on a daily basis).

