An in-depth understanding of OA pathophysiology is still emerging [1]. Recently, angiogenesis has been implicated in OA by contributing to structural damage, inflammation and pain [10]. Angiogenesis is blood vessel overgrowth from pre-existing vasculature and is essential for growth, development and tissue repair [10]. However, in OA, angiogenesis increases in articular cartilage, synovium, meniscus, and osteophytes, and at the osteochondral junction [11-15]. Because angiogenesis is accompanied by sensory nerve growth, perivascular nerve growth into normally aneural structures such as articular cartilage and meniscus is thought to contribute to OA pain through chemical and mechanical stimulation of newly formed nerves. Modifying angiogenesis and associated nerve growth is a potential treatment pathway to affect the pathogenesis and symptoms of OA [10]. Angiogenesis inhibitor treatment decreased pain-related behavior in animal models [11]. The mechanism of symptomatic relief is unclear but could include reduced synovitis, reduced periarticular innervation and nociception, and maintaining the integrity of the osteochondral junction [10, 11].

A recent study by Padia S et al evaluated the safety and effectiveness of GAE in patients with knee OS (grades 2, 3, 4). Knee OA severity was grade 2 in 18% of the patients, grade 3 in 43%, and grade 4 in 40%. Technical success was achieved in 100% of the subjects. The WOMAC total and VAS pain scores decreased by 61% and 67% at 12 months from a median baseline of 52 (of 96) and 8 (of 10), respectively. Twenty-seven patients (68%) had a reduction of $\geq 50\%$ in both WOMAC total and VAS pain scores [32]. The WOMAC questionnaire is a widely used, disease-specific measure for knee OA. It includes 24 questions on daily activities: five regarding pain, two regarding stiffness, and 17 regarding physical function; possible score ranges for each subset of items are as follows: pain, 0–20; stiffness, 0–8; and physical function, 0–68. For each question in each of the three categories (pain, stiffness, and physical function) patients receive the following points: 0 for no symptoms, 1 for mild, 2 for moderate, 3 for severe, and 4 for extreme symptoms. Higher scores on the WOMAC indicate worse pain, stiffness, and functional limitation [16].

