5.7 Participant Withdrawal or Termination

5.7.1 Reasons for Withdrawal or Termination

Participants are free to withdraw from participation in the study at any time upon request. Participation of a patient in this clinical study may be discontinued for any of the following reasons:

- The patient withdraws consent or requests discontinuation from the study for any reason;
- Occurrence of any medical condition or circumstance that exposes the patient to substantial risk and/or does not allow the patient to adhere to the requirements of the protocol;
- Any AE, clinically significant adverse event, severe laboratory abnormality, intercurrent illness, or other medical condition that indicates to the investigator that continued participation is not in the best interest of the patient;
- Pregnancy during study period;

CONFIDENTIAL

- Patient failure to comply with protocol requirements or study-related procedures;
- Termination of the study by the Sponsor, the regulatory authority, FDA, or IRB.
- The participant meets an exclusion criterion (either newly developed or not previously recognized) that precludes further study participation
- Progression of osteoarthritis requiring surgical therapy
- Patients found to have osteonecrosis on pre-procedural MRI

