5.7.2 Handling of Participant Withdrawals or Termination

If a patient withdraws prematurely from the study due to the above criteria or any other reason, study staff should make every effort to complete the full panel of assessments scheduled for the follow-up visits. The reason for patient withdrawal must be documented in the electronic case report form (eCRF). In the case of loss of follow-up, attempts to contact the patient will be made and documented in the patient's medical records. Every effort will be made to undertake protocol-specified safety follow-up procedures to capture AEs, serious adverse events (SAEs), and unanticipated problems (UPs).

Withdrawn patients can be replaced.

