10.3 Analysis Datasets

Participants who complete all follow-up visits will be included in the study.

CONFIDENTIAL

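### Technical success is known on day 0 but, as written, would be computed only in 12-month completers; separately, 6.1.5 and 6.2 set different minimum end points for the same injection

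*Combined protocol and SAP*

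**What the plan says.** **Definition and timing.** Section 3.2 makes feasibility, or technical success, a secondary objective. It requires selective catheterization of the target vessel(s) and embolization of at least one artery feeding the knee joint. The angiographic end point is that the abnormal vessels fill less or not at all. Section 10.4.3 restates the outcome as "the technical success rate (defined as the proportion of patients for whom the procedure was successfully completed", without pointing to 3.2 and without a denominator. Treatment is a single session on day 0 (6.1.7), and the angiogram repeated after embolization is used to judge success (6.2).

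**Analysis set.** Section 10.3 is one sentence: "Participants who complete all follow-up visits will be included in the study". The last required visit is at 12 months (5.5); the visit at 18 to 48 months is optional (7.3.5). No treated, procedural or safety set is defined, and 10.1 states that no formal SAP will be prepared before database lock.

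**Withdrawals.** Section 5.7.2 says "Withdrawn patients can be replaced". It also says that after a withdrawal "study staff should make every effort to complete the full panel of assessments scheduled for the follow-up visits". The reasons for discontinuation in 5.7.1 include "Progression of osteoarthritis requiring surgical therapy" and "Patients found to have osteonecrosis on pre-procedural MRI".

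**Injection end point.** Section 6.1.5 has the operator inject until flow in the target artery stagnates. Section 6.2 gives the same volumes and timing but asks for at least pruning of the hypervascular synovium, explained as slowed forward flow.

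**The concern.** Technical success is the feasibility measure of a study that 4.1 describes as evaluating safety and feasibility. Its value is fixed when the patient leaves the angiography suite, and attendance at month 12 carries no information about it. Applying the completer rule discards day-0 results that are already known. If technical failures leave the study more often than other patients, the reported rate is too high; if they leave less often, it is too low. Replacement makes this harder to see, because a patient who fails and is replaced appears in neither numerator nor denominator.

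The injection end points raise a smaller, separate matter. A case stopped at slowed flow complies with 6.2 and deviates from 6.1.5. Section 14.3 requires all protocol deviations to be reported to the PI, IRB and FDA, so it is unclear whether such a case is reportable.

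**Working it through.** **1. The plan's own figures.** Sections 5.6 and 10.5 ask for data from 40 patients with 20% attrition: 40 / (1 - 0.20) = 50. This reproduces. The expected number of non-completers is 50 - 40 = 10. The FDA letter described in 2.2 limits the study to 50 subjects, so at most 50 patients can be attempted.

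**2. How many failures are plausible.** The documents give no expected number for this study. Both technical success rates they cite are 100%: the knee OA series in 2.1 ("Technical success was achieved in 100% of the subjects") and the series on hemorrhage after arthroplasty in 2.2.2. The size of the knee OA series follows from "Twenty-seven patients (68%) had a reduction of" at least half on both scores: 27/40 = 67.5%, which rounds to 68%, whereas 27/39 = 69.2% and 27/41 = 65.9% do not. With 0 failures in 40, the exact 95% upper limit is 1 - 0.025^(1/40) = 8.8%, and 0.088 x 50 = 4.4. The best guess is therefore 0 failures and the outer limit is 4, if that series is comparable. I use 1 to 2 in 50 as an assumed working range.

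**3. Completer rate against all-attempted rate.** Let f be the number of failures and w the number of those who do not complete. Assume that all 10 losses come after arterial access.

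- All attempted: (50 - f)/50
- Completers: (40 - (f - w))/40

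| f | w | All attempted | Completers | Difference |
|---|---|---|---|---|
| 0 | 0 | 50/50 = 100% | 40/40 = 100% | 0 |
| 1 | 0 | 49/50 = 98.0% | 39/40 = 97.5% | -0.5 points |
| 1 | 1 | 49/50 = 98.0% | 40/40 = 100% | +2.0 points |
| 2 | 0 | 48/50 = 96.0% | 38/40 = 95.0% | -1.0 points |
| 2 | 1 | 48/50 = 96.0% | 39/40 = 97.5% | +1.5 points |
| 2 | 2 | 48/50 = 96.0% | 40/40 = 100% | +4.0 points |

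If failures drop out with probability r, the expected difference is f(r - 0.20)/40. This is zero at r = 0.20, the planned attrition for everyone. At r = 0.40 it is +0.5 points for f = 1 and +1.0 point for f = 2.

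**4. Losses before access.** Some of the 10 may leave before the procedure, for example through osteonecrosis on the baseline MRI. If only 5 losses follow access, 45 are attempted. With f = 2 the all-attempted rate is 43/45 = 95.6%, and the completer rate runs from 38/40 = 95.0% (-0.6) to 40/40 = 100% (+4.4). The range hardly moves.

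**5. Scale.** The exact 95% interval is 91.2% to 100% for 40/40 and 86.3% to 99.5% for 48/50. Even a 4-point shift is small beside the sampling uncertainty.

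**6. The two end points beside 3.2.** Stagnation satisfies 6.1.5 and 6.2. Slowed flow satisfies 6.2 and can satisfy 3.2, where reduced filling is enough, but not 6.1.5. The minimum required therefore differs between the two sections. No effect on a result can be computed from the documents.

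**The case against.** The strongest reply is that 10.4.3 speaks of patients in whom the procedure was completed, so its natural denominator is everyone who had it. On this view 10.3 is one loose sentence that assigns no endpoint to any set. That reading is reasonable and may be what was meant. Nothing written says so, however, and with no formal SAP planned, no later document would settle it.

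It is also fair that bias needs both failures and a link between failure and dropout. No section makes a failed procedure a reason to withdraw, progression to surgery is not tied to technical failure, and 5.7.2 asks staff to complete assessments after withdrawal. This stands, and it is why the size is given as a range that includes zero.

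Three stronger readings are tempting and should be resisted:

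- **An 8 to 9 point overstatement.** A reader might infer this by taking 4 failures, all of whom drop out: 100% - 46/50 = 8.0 points, or 100% - 41/45 = 8.9 points. It needs the upper limit of a zero-failure series and complete dropout among failures. The documents support neither.
- **No way to classify a patient without abnormal neovessels.** Section 3.2 requires embolization of at least one feeding artery, so a patient who is not embolized is already a non-success.
- **The stopping-point conflict distorts technical success.** Section 3.2 accepts reduced filling and does not require stagnation. What remains is an inconsistency in drafting and in how deviations are labelled.

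Finally, the completer rule matters more for the primary response and adverse events. That is correct, and correcting technical success alone does not resolve it.

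**Conclusion.** The concern holds as a minor one. As written, a day-0 outcome would be computed only in 12-month completers, at the cost of up to 10 of 50 known results. The difference from the all-attempted rate is zero with no failures, or when failure is unrelated to dropout. It is about -1 to +4 points with 1 to 2 failures. This rests on 50 accrued and 40 completing, on the assumed failure count, and on most losses coming after access. The direction is not determined by the documents. The decision rule in 10.2 uses clinical response only, so no trial conclusion depends on this rate.

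The conflict between 6.1.5 and 6.2 is real but secondary; it bears on which cases count as deviations, with no demonstrated effect on any analysis.

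**What to change.** - **10.3:** state that technical success is analyzed in all patients in whom arterial access was attempted, regardless of later follow-up, withdrawal or replacement.
- **10.4.3:** replace the parenthesis with a reference to the definition in 3.2, judged on the post-embolization angiogram. A patient not embolized because no abnormal neovessels are found then counts as a non-success; reporting that count separately is optional.
- **6.1.5 and 6.2:** state one minimum end point in both. The 6.2 wording fits 3.2, subject to the sponsor confirming it against the IDE, which is not among the documents reviewed.
- **Separately:** when 10.3 is revised, set the denominators for the primary response and the adverse event rate. The changes above do not do this.

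The cost is wording only, with no extra patients, visits or data. The reported technical success rate may shift slightly in either direction. If the common end point is worded as a minimum, cases may still range from slowed flow to stagnation.
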